2.1.2. Handling Missing Data

In order to provide unbiased and informative findings, no replacement of missing values is planned for any parameters. Analyses is performed with all available data only.

Data collected by the Investigators and reviewed by the Clinical Event Committee (CEC):

CONFIDENTIEL / CONFIDENTIAL

Toute reproduction ou distribution, totale ou partielle, de ce document, sans autorisation préalable de ICON PLC est interdite.
Reproduction and distribution of this document, in whole or in part, is strictly forbidden without prior authorization from ICON PLC.

	STATISTICAL ANALYSIS PLAN	FARAPULSE PersAFOne SAP V1.0 PERSAFONE Page 13 /49
---	----------------------------------	--

When the data are collected by the investigators and reviewed by the CEC, the analysis will be as follows:

- The data reviewed by the CEC will prevail and will be analysed with no replacement of missing data from the CEC with the data collected by the investigator

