2.1.3. Descriptive Statistics in Summary Tables

- *Continuous variables* will be summarized using standard quantitative statistics: number of non-missing observations, mean, standard deviation, median, quartiles and range (minimum and maximum observed values). The number of missing observations will also be specified.
- *Categorical variables* will be summarized using classical frequency statistics: number of non-missing observations and percentages by categories. Percentages will be calculated on the number of non-missing observations and will be displayed using one decimal. The number of missing observations will also be specified.

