2.5. Derived Criteria Calculation

If at least one of the items needed to calculate a derived criteria is missing, then the corresponding derived criteria will be considered as missing.

Patient Disposition:

- Derived criteria “Enrolled population” will be analysed as:
IF the date of patient consent is filled in **Patient eligibility form (IE)** **THEN** “Enrolled population” = ‘Yes’
ELSE “Enrolled population” = ‘No’.
- Derived criteria “ITT population” will be defined as follows:
IF “Enrolled population” = ‘Yes’ in **Patient eligibility form (IE)** and the date of the Procedure is filled in **Procedural data form (PR)** **THEN** “ITT population” = ‘Yes’
ELSE “ITT population” = ‘No’.
- Derived criteria “Per Protocol population PP” will be defined as follows:
IF “ITT population” = ‘Yes’ **AND** Device Deficiency Number is not filled **AND** Serial # is not filled in **Device Deficiency DD Form** **THEN** Per Protocol population = ‘Yes’
ELSE Per Protocol population = ‘No’.
- Derived criteria “Time of patient follow-up” will be calculated as:
Date of study exit/withdrawal (*) in **Patient eligibility form (IE)** – date of procedure in **Procedural data form (PR)**
*if the patient is still in the study, the last visit date will be used instead of the exit/ withdrawal one.
- Derived criteria “COVID status” will be calculated as:
IF “Related to COVID-19 situation” =1 **OR** the term “COVID” exist in “reason for deviation” **AND** date of deviation is filled in **Protocol deviation form (PD)**, **THEN** CLASS=“ COVID-19”
ELSE IF date of deviation is filled **THEN** CLASS= “NOT COVID-19”.

Baseline Patient Characteristics:

- Derived criteria “Time from first AF diagnosis until consent date (months)” will be defined as follows:
Informed consent date – date of first documented AF diagnosis in **AF history form (AH)**.
- Derived criteria “Time between the most recent AF episode and the enrollment (months)” will be defined as follows:
Informed consent date – date of most recent AF episode in **AF history form (AH)**.
- Derived criteria “Permanent pacemaker or ICD” will be defined as follows:
IF Pacemaker, Implantable Cardioverter Defibrillator or Cardiac Resynchronization therapy device= ‘Yes’ in **Patient eligibility Form (IE)** **THEN** Permanent pacemaker or ICD=‘Yes’

CONFIDENTIEL / CONFIDENTIAL

Toute reproduction ou distribution, totale ou partielle, de ce document, sans autorisation préalable de ICON PLC est interdite.

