COUNT of ["left superior", "left inferior", "left common ostium", "right middle", "right superior", "right inferior"] **WHERE** isolated/Blocked in ('Yes', 'No') in **Procedural data form (PR)**
- Derived criteria "Total number of veins isolated" will be defined as follows:
SUM of [left superior, left inferior, left common ostium, right middle, right superior, right inferior] **WHERE** isolated/Blocked = 'Yes' in **Procedural data form (PR)**

CONFIDENTIEL / CONFIDENTIAL

Toute reproduction ou distribution, totale ou partielle, de ce document, sans autorisation préalable de ICON PLC est interdite.
Reproduction and distribution of this document, in whole or in part, is strictly forbidden without prior authorization from ICON PLC.

	STATISTICAL ANALYSIS PLAN	FARAPULSE PersAFOne SAP V1.0 PERSAFONE Page 21 /49
---	----------------------------------	--

- Derived criteria "Of the total number of veins treated, the number of veins isolated (Proportion of veins isolated)" will be defined as follows:
Derived criteria "Total number of veins isolated"/ Derived criteria "Total number of veins treated"
- Derived criteria Proportion "CTI acute isolation" will be defined as follows:
COUNT of [CTI isolated/Blocked='Yes' /CTI Attempted='Yes'] in **Procedural data form (PR)**

Remapping at 75 Days

- Derived criteria "Days follow up at remap" will be defined as follows:
Remapping date – Date of index procedure
- Derived criteria "Durable PVI" will be defined as follows:
IF Left Superior Lesion durable='Yes' **AND** Left Inferior Lesion durable='Yes' **AND** Left Common Ostium Lesion durable='Yes' **AND** Right Middle Lesion durable='Yes' **AND** Right Superior Lesion durable='Yes' **AND** Right Inferior Lesion durable='Yes' **AND** CTI Lesion durable='Yes' **AND** Mitral Isthmus Lesion durable='Yes' **AND** Left Atrial Roof Line Lesion durable='Yes' **AND** Left Atrial Posterior Line Lesion durable='Yes' **AND** Other 1 Lesion durable='Yes' in **Follow-up 3D electroanatomical mapping form (RM)** **THEN** Durable PVI='Yes'
ELSE Durable PVI='No'
- Derived criteria "LAPW chronic isolation" will be defined as follows:

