IF Anatomical Structure/Area other specification 1 **IN** ("POSTERIOR WALL" "LA POSTERIOR WALL" "LAPW" "PA WALL" "BOX POSTERIOR WALL") **AND** Other 1 Lesion durable = 'yes' **OR** Anatomical Structure/Area other specification 2 **IN** ("POSTERIOR WALL" "LA POSTERIOR WALL" "LAPW" "PA WALL" "BOX POSTERIOR WALL") **AND** Other 2 Lesion durable = 'Yes' in **Follow-up 3D electroanatomical mapping form (RM)** **THEN** LAPW chronic isolation= 'Yes'
ELSE LAPW chronic isolation = 'No'
- Derived criteria "Number of veins durably isolated" will be defined as follows:
SUM of [LSPV chronic isolation='Yes', LIPV chronic isolation='Yes', LCPV chronic isolation='Yes', RSPV chronic isolation='Yes', RIPV chronic isolation='Yes', RMPV chronic isolation ='Yes'] in **Follow-up 3D electroanatomical mapping form (RM)**
- Derived criteria "Number of veins with gaps" will be defined as follows:
SUM of [LSPV chronic isolation='No', LIPV chronic isolation=' No', LCPV chronic isolation=' No', RSPV chronic isolation=' No', RIPV chronic isolation=' No', RMPV Chronic isolation = 'No'] in **Follow-up 3D electroanatomical mapping form (RM)**

6 and 12 Months follow up

- Derived criteria "TTM compliance (%) (calculated)" will be defined as follows:
(TTM weeks received /TTM weeks expected) *100 in **MDT excel file**
- Derived criteria "Holter compliance (%) at 6 months" will be defined as follows:

CONFIDENTIEL / CONFIDENTIAL

Toute reproduction ou distribution, totale ou partielle, de ce document, sans autorisation préalable de ICON PLC est interdite.
Reproduction and distribution of this document, in whole or in part, is strictly forbidden without prior authorization from ICON PLC.

	STATISTICAL ANALYSIS PLAN	FARAPULSE PersAFOne SAP V1.0 PERSAFONE Page 22 /49
---	----------------------------------	--

IF 6mo Holter in ('AF', 'none', 'SVT') in **MDT excel file** **THEN** Holter compliance (%) at 6 months = 'Yes'

ELSE IF 6mo Holter in ('MISSING') in **MDT excel file** **THEN** Holter compliance (%) at 6 months='No'

- Derived criteria "Holter compliance (%) at 12 months" will be defined as follows:

IF 12mo Holter in ('AF', 'none', 'SVT') in **MDT excel file** **THEN** Holter compliance (%) at 12 months = 'Yes'

ELSE IF 12mo Holter in ('MISSING') in **MDT excel file** **THEN** Holter compliance (%) at 12 months='No'

- Derived criteria "Freedom from AF/AFL/AT" will be defined as follows:

IF AF/AFL/AT status =0 in **MDT excel file** **THEN** Freedom from AF/AFL/AT ='Yes'

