COUNT of [(Left Superior Isolated/Blocked ='Yes', Left Inferior Isolated/Blocked='Yes', Left Common Ostium Isolated/Blocked='Yes', Right Middle Isolated/Blocked='Yes', Right Superior Isolated/Blocked='Yes', Right Inferior Isolated/Blocked='Yes')] / COUNT of [(Left Superior Isolated/Blocked in (Yes, No) , Left Inferior Isolated/Blocked in (Yes, No), Left Common Ostium Isolated/Blocked in (Yes, No), Right Middle Isolated/Blocked in (Yes, No), Right Superior Isolated/Blocked in (Yes, No), Right Inferior Isolated/Blocked in (Yes, No))] **in Procedural data form (PR)**
- Derived criteria "Proportion of all ablated pulmonary veins isolated using the study device during the Index Procedure that remain isolated at the 75-day remapping procedure" will be defined as follows:
(Derived criteria "Total number of veins isolated" - Derived criteria "Number of veins with gaps")/ Derived criteria "Total number of veins isolated"
- Derived criteria Proportion "Chronic CTI at 75d remap" will be defined as follows:
IF CTI lesion durable ='Yes' **in Follow-up 3D electroanatomical mapping form (RM)** **THEN** Chronic CTI at 75d remap ='Yes'
ELSE IF CTI lesion durable ='No' **in Follow-up 3D electroanatomical mapping form (RM)** **THEN** Chronic CTI at 75d remap ='No'
- Derived criteria Proportion "LAPW chronic isolation" will be defined as follows:
IF Anatomical Structure/Area other specification 1 **IN** ("POSTERIOR WALL" "LA POSTERIOR WALL" "LAPW" "PA WALL" "BOX POSTERIOR WALL") **AND** Other 1 Lesion durable = 'yes' **OR** Anatomical Structure/Area other specification 2 **IN** ("POSTERIOR WALL" "LA POSTERIOR WALL" "LAPW" "PA WALL" "BOX POSTERIOR WALL") **AND** Other 2 Lesion durable = ='Yes' **in Follow-up 3D electroanatomical mapping form (RM)** **THEN** LAPW chronic isolation= 'Yes'

CONFIDENTIEL / CONFIDENTIAL

Toute reproduction ou distribution, totale ou partielle, de ce document, sans autorisation préalable de ICON PLC est interdite.
Reproduction and distribution of this document, in whole or in part, is strictly forbidden without prior authorization from ICON PLC.

	STATISTICAL ANALYSIS PLAN	FARAPULSE PersAFOne SAP V1.0 PERSAFONE Page 26 /49
---	----------------------------------	--

ELSE LAPW chronic isolation = 'No'

Primary Safety endpoint

Unless otherwise indicated, all the following variables will be derived from the Adverse event adjudication form (CE)

- Derived criteria "Death" will be defined as follows:

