4.1.6. Table 6. Per Remapped Veins Analysis

	Veins Remapped N = XX	
	n/N (%)	[95% CI]
Number of veins durably isolated	XX/XX (XX.X%)	[XX% - XX%]
Number of veins with gaps	XX/XX (XX.X%)	[XX% - XX%]
Missing Data	XX	NA

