4.1.11. Table 11. Additional Endpoints

ITT Population		
N = XX		
	Mean±S.D.	
	Median (min, max) (Q1, Q3)	[95% CI]
Time to Therapeutic Failure (days)	XX±X XX (XX, XX) (XX, XX)	[XX - XX]
	n/N (%)	[95% CI]
Proportion of subjects with Early recurrence of atrial fibrillation (ERAF) by 90 days after the index procedure	XX/XX (XX.X%)	[XX% - XX%]
Proportion of all ablated pulmonary veins that are isolated at the Index Procedure using the study device	XX/XX (XX.X%)	[XX% - XX%]
Proportion of all ablated pulmonary veins isolated using the study device during the Index Procedure that remain isolated at the 75-day remapping procedure	XX/XX (XX.X%)	[XX% - XX%]

CONFIDENTIEL / CONFIDENTIAL

Toute reproduction ou distribution, totale ou partielle, de ce document, sans autorisation préalable de ICON PLC est interdite.
Reproduction and distribution of this document, in whole or in part, is strictly forbidden without prior authorization from ICON PLC.

	STATISTICAL ANALYSIS PLAN	FARAPULSE PersAFOne SAP V1.0 PERSAFONE Page 42 /49
---	----------------------------------	--

The proportion of attempted subjects that achieve Chronic CTI Success, defined as persistent bi-directional electrical block across the CTI assessed at the 75-day Remapping Procedure	XX/XX (XX.X%)	[XX% - XX%]
The proportion of attempted subjects that achieve Chronic Focal Success, defined as persistent electrical nonconductivity of all extra-PV tissue targeted for ablation in the Index Procedure, excluding the CTI	XX/XX (XX.X%)	[XX% - XX%]

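### The Table 11 vein-durability formula counts a vein isolated at index but never remapped as still isolated

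*SAP*

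**What the plan says.** The last vein-level row of SAP Table 11 reports ablated veins isolated with the study device "during the Index Procedure that remain isolated at the 75-day remapping procedure". Section 2.5 (Additional endpoints) computes it as "Derived criteria 'Total number of veins isolated' - Derived criteria 'Number of veins with gaps')/ Derived criteria 'Total number of veins isolated".

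Its two inputs are defined elsewhere in section 2.5:

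- Under Index Procedure, "Derived criteria 'Total number of veins isolated' will be defined as follows": a count of the six named vein positions recorded as isolated on the index procedural form, with no condition on remapping.
- Under Remapping at 75 Days, "Derived criteria 'Number of veins with gaps' will be defined as follows": a count of the same six positions recorded as No on the remap form. A blank adds nothing.

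The rules that bear on this are:

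- SAP 2.1.2: no replacement of missing values, and "Analyses is performed with all available data only". Protocol 5.5 says the same.
- SAP 2.1.3: "Percentages will be calculated on the number of non-missing observations".
- SAP 2.5, opening sentence: "If at least one of the items needed to calculate a derived criteria is missing", the derived criterion is itself treated as missing.
- SAP Table 6: the base is "Veins Remapped N = XX", with a separate line for missing data.
- SAP 2.4.7: the additional endpoints are run on the ITT population, with no restriction to remapped subjects.
- SAP Table 13: the patient-level counterpart, Chronic Procedural Success (CPS), is restricted to subjects who had the remap.

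Protocol 3.12.5 schedules the remap for all subjects but also gives instructions for subjects who do not have it, including those who decline.

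**The concern.** The formula takes its starting count from one visit and subtracts failures seen at another. That is a proportion only if every vein in the starting count was examined at the second visit. A vein that was not examined cannot be recorded as a gap, so the subtraction leaves it among the successes. A patient with four isolated veins and no remap contributes 4/4.

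This amounts to imputing success, which the SAP says it will not do. The error favours the device, and the larger N gives the rate more apparent precision than the data support. SAP 2.2 says the results will inform the design of further studies, and durability at remap is the kind of figure likely to be carried forward.

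**Working it through.** The plan states no figure to reproduce; the Table 11 row is an empty shell. The check is algebra on the SAP's definitions, followed by illustrations.

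**Algebra.** Let I be veins isolated at index, R those of them with a remap result, and G the gaps found, all taken to lie among the R veins.

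- As written: F = (I − G)/I.
- On available data: A = (R − G)/R.
- Since I − G = (R − G) + (I − R), every vein without a result is added to the successes.
- With p = A and r = R/I, F = 1 − r(1 − p), so the excess is F − A = (1 − p)(1 − r). It is never negative, and it is zero when r = 1 or p = 1.

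**Single-patient check.** Four veins are isolated at index; at remap two are durable, one has a gap and one is blank. As written: (4 − 1)/4 = 75.0%. Available data: 2/3 = 66.7%.

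**Plausible size.** The documents give no remap share or durability for this study. Protocol 1.3.1 and 1.3.2 give both for the earlier studies. The patient remap share is taken as the vein share, which is an assumption.

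| Source | p | r | As written | Excess |
|---|---|---|---|---|
| Protocol 1.3.1 | 0.70 | 35/40 = 0.875 | 73.75% | 0.30 × 0.125 = 3.75 points |
| Protocol 1.3.2 | 0.96 | 49/60 = 0.817 | 96.73% | 0.04 × 0.183 = 0.73 points |

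With equal vein counts, each un-remapped patient out of 40 adds 0.30/40 = 0.75 points at 70% durability, or 0.04/40 = 0.10 at 96%.

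**Illustrations** (40 patients, four veins each, all 160 isolated at index; exact 95% intervals).

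| Case | Available data | As written |
|---|---|---|
| (a) 35 remapped, 42 gaps | 98/140 = 70.0% (61.7–77.4) | 118/160 = 73.8% (66.2–80.4) |
| (b) 33 remapped, 5 gaps | 127/132 = 96.2% (91.4–98.8) | 155/160 = 96.9% (92.9–99.0) |

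**Does the missing-item rule repair it?** The SAP does not say at what level the rule applies. On case (a):

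- Applied to the pooled totals, neither of which is missing: 73.8%, so the inflation stays.
- Applied per patient to the veins that patient has: 70.0%, so the inflation goes.
- Applied per patient to all six listed positions: nobody is evaluable, because a four-vein patient always has two blank fields.

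The gap count works for ordinary anatomy only if blanks add zero, and that same convention produces the inflation.

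**An error in the other direction.** The gap count is not limited to veins isolated at index. If 159 of 160 treated veins were isolated and the remaining one is marked No at remap, it is wrongly subtracted and the rate falls by 1/159 = 0.6 points. This is hypothetical: both earlier studies report all veins isolated at index.

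**The case against.** The strongest reply is that the missing-item rule opens section 2.5 and therefore governs this formula. The only non-remapping the protocol describes is a whole patient who is not remapped. Applied patient by patient, the rule would drop that patient and the inflation with it, so the fault would be ambiguity rather than error. It is also fair that other readings exist: the six-field reading removes the inflation too, by removing everyone, and a strictly literal pooled reading could make the whole ratio missing. What stands is that the outcome depends on a choice the SAP does not make. The one reading that gives a usable and correct rate needs two conditions that are nowhere written: per patient, and present veins only.

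Second, the row label and the matching item in Protocol 6.5 take all index-isolated veins as the base, so the denominator agrees with the label. That is right. The conflict with the label lies in the numerator, since a vein not examined cannot be said to remain isolated at remap. The case for the smaller base rests on SAP 2.1.2 and 2.1.3 and Protocol 5.5.

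Third, the size is uncertain and may be small. The 3.8-point figure comes from a study remapped at 3 months, while the study with this trial's 75-day timepoint gives 0.7. Both remap counts were still accruing, so the final shares could be higher. In the other direction, the shells for Tables 5 and 19 print N = 25; at that size each un-remapped patient adds 0.30/25 = 1.2 points at 70% durability, or 0.04/25 = 0.16 at 96%.

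Finally, Table 6 already reports remapped veins correctly and CPS ranks above this row. That limits the harm, but the same report could then carry two vein-durability rates that differ for no stated reason.

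**Conclusion.** The concern holds. As written, the formula counts un-remapped veins as durable, against the SAP's own rules. The excess is (1 − p)(1 − r): about 3.8 points with the first earlier study's figures and 0.7 with the second's, if patient remap share stands in for vein share. It vanishes if every index-isolated vein is remapped or no gap is found.

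Tables 6 and 11 may legitimately differ in N, because remapped veins and index-isolated veins are different sets, but un-remapped veins should not be part of that difference. This is an additional descriptive assessment with no test or decision rule, so it should be corrected but threatens no primary conclusion.

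**What to change.** In SAP 2.5 (Additional endpoints), define the denominator as veins isolated at index that have a Yes or No result at remap, and the numerator as those same veins recorded as isolated at remap. This removes the error in both directions. Add one sentence saying that a vein the patient does not have, such as a left common or right middle vein, is not a missing item under the general rule. Footnote Table 11 with the number of index-isolated veins not remapped and the reason for any difference from the Table 6 N.

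The cost is one formula, one sentence and one footnote. No new data are needed. The downside is a smaller N and possibly a lower rate.

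A separate, optional point: the binomial intervals for the vein-level rows of Tables 4, 6 and 11 are too narrow if veins within a patient are positively correlated. The earlier studies disagree on this. The first (70% of veins, 14 of 35 patients fully isolated, four veins assumed) is compatible with a design effect anywhere from 1.14 to 2.57. The second (five veins assumed, since ten patients with a gap among 49 × 4 = 196 veins would cap durability at 94.9%) gives 0.83 or 1.00, depending on whether there were 10 or 11 gaps. A patient-clustered interval could be added as a sensitivity analysis. At 0% or 100%, keep the vein-level row; a patient-level exact interval may stand beside it, labelled as a different quantity.

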6.4 Secondary Feasibility Endpoints

1. The proportion of subjects who undergo the protocol-specified 75-Day Remapping Procedure and achieve Chronic Procedural Success (CPS) defined as persistent electrical isolation of all initially ablated pulmonary veins. Chronic Procedural Success will be subdivided by Index Procedure only CPS and Reablated CPS subjects.

2. The proportion of attempted subjects that achieve Acute CTI Success, defined as the creation of bi-directional electrical block across the CTI using the investigational devices.
3. Durability of the CTI and/or other extra-PV lesion set(s), when applicable. Durability is defined as unaltered integrity of each such lesion assessed at the Remapping Procedure.
4. The proportion of subjects that achieve Therapeutic Success, defined as freedom from:
 - a. Post-Blanking Period through assessment: occurrence of AF, AFL or AT, or ablation for AF/AFL/AT using the study device
 - b. At any time: ablation for AF/AFL/AT with a nonstudy deviceTherapeutic Success will be assessed from the end of the 90 Day Blanking Period through Months 6 and 12 and will be subdivided by on / off AFDs (Atrial Fibrillation Drugs) post-Blanking Period.

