6.5 Additional Assessments

1. Proportion of subjects with early recurrence of atrial fibrillation (ERAF) by 90 days after the initial study ablation.
2. Time to Therapeutic Failure
3. Proportion of all ablated pulmonary veins that are isolated at the Index Procedure using the study device.
4. Proportion of all ablated pulmonary veins isolated using the study device during the Index Procedure that remain isolated at the 75-day Remapping Procedure.
5. The proportion of attempted subjects that achieve Chronic CTI Success, defined as persistent bi-directional electrical block across the CTI as assessed at the 75-day remapping procedure.
6. The proportion of attempted subjects that achieve Chronic Focal Success, defined as persistent electrical nonconductivity of extra-PV tissue targeted for ablation in the Index Procedure, excluding the CTI

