2.4.6.2. Secondary Feasibility Analysis

The secondary feasibility analyses are:

- The proportion of subjects who undergo the protocol-specified 75-Day Remapping Procedure and achieve Chronic Procedural Success (CPS) defined as persistent electrical isolation of all initially ablated pulmonary veins. Chronic Procedural Success will be subdivided by Index Procedure only CPS and Reablated CPS subjects.
- The proportion of attempted subjects that achieve Acute CTI Success, defined as the creation of bi-directional electrical block across the CTI using the investigational devices.
- Durability of the CTI and/or other extra-PV lesion set(s), when applicable.
Durability is defined as unaltered integrity of each such lesion assessed at the Remapping Procedure.
- The proportion of subjects that achieve Therapeutic Success, defined as freedom from:
 - Post-Blanking Period through assessment: occurrence of AF, AFL or AT, or ablation for AF/AFL/AT using the study device
 - At any time: ablation for AF/AFL/AT with a non-study device
Therapeutic Success will be assessed from the end of the 90 Day Blanking Period through Months 6 and 12 and will be subdivided by on / off AADs (Atrial Fibrillation Drugs) post-Blanking Period.

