2.4.7. Additional endpoints

The additional observations will be performed on the ITT population and will include:

- Proportion of subjects with early recurrence of atrial fibrillation (ERAF) by 90 days after the initial study ablation.
- Time to Therapeutic Failure
- Proportion of all ablated pulmonary veins that are isolated at the Index Procedure using the study device.
- Proportion of all ablated pulmonary veins isolated using the study device during the Index Procedure that remain isolated at the 75-day Remapping Procedure.
- The proportion of attempted subjects that achieve Chronic CTI Success, defined as persistent bi-directional electrical block across the CTI as assessed at the 75-day remapping procedure.
- The proportion of attempted subjects that achieve Chronic Focal Success, defined as persistent electrical nonconductivity of extra-PV tissue targeted for ablation in the Index Procedure, excluding the CTI

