Toute reproduction ou distribution, totale ou partielle, de ce document, sans autorisation préalable de ICON PLC est interdite.
Reproduction and distribution of this document, in whole or in part, is strictly forbidden without prior authorization from ICON PLC.

	STATISTICAL ANALYSIS PLAN	FARAPULSE PersAFOne SAP V1.0 PERSAFONE Page 24 /49
---	----------------------------------	--

ELSE IF Ablation with study device was successful = 'No' in **procedural form (PR)** **THEN**
APS='No'

Secondary Feasibility Analysis

- Derived criteria "Chronic Procedural Success (CPS)" will be defined as follows:
IF Has all ablation with the study device(s) been successful? ='Yes' in **Procedural data form (PR)** **AND** Has all ablation with the study device remain successful? ='Yes' **AND** Additional ablation(s) performed? ='No' in **FOLLOW UP 3D ELECTRO ANATOMICAL MAPPING form (RM)** **THEN** Chronic Procedural Success (CPS) ='Yes, index procedure only'
ELSE IF Has all ablation with the study device(s) been successful? ='Yes' in **Procedural data form (PR)** **AND** Has all ablation with the study device remain successful? ='No' **AND** Any PV reconnections noted? in = 'Yes' **AND** Additional ablation(s) performed? ='Yes' in **FOLLOW UP 3D ELECTRO ANATOMICAL MAPPING form (RM)** **THEN** Chronic Procedural Success (CPS) ='Yes, reblated'
ELSE IF Has all ablation with the study device(s) been successful? ='No' in **Procedural data form (PR)** **THEN** Chronic Procedural Success (CPS) ='No'
- Derived criteria Proportion "Acute Cavotricuspid isthmus (CTI) Success" will be defined as follows:
COUNT IF [CTI isolated/Blocked='Yes' AND CTI Attempted='Yes'] in **Procedural data form (PR)**
- Derived criteria "Durability of CTI at remap," will be defined as follows:
IF CTI lesion durable ='Yes' in **Follow-up 3D electroanatomical mapping form (RM)** **THEN** Durability of CTI at remap = 'Yes'
ELSE IF CTI lesion durable ='No' in **Follow-up 3D electroanatomical mapping form (RM)** **THEN** Durability of CTI at remap = 'No'
- Derived criteria "Durability of Mitral isthmus at remap" will be defined as follows:
IF Mitral isthmus lesion durable ='Yes' in **Follow-up 3D electroanatomical mapping form (RM)** **THEN** Durability of Mitral isthmus at remap = 'Yes'
ELSE IF Mitral isthmus lesion durable ='No' in **Follow-up 3D electroanatomical mapping form (RM)** **THEN** Durability of Mitral isthmus at remap = 'No'

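### SAP 2.5 derives Chronic CTI Success and CTI durability by one identical rule, which cannot serve both when a remapped subject's CTI was attempted but not blocked at index

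*SAP*

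**What the plan says.** **Chronic CTI Success.** Protocol 6.5, item 5, defines it as "The proportion of attempted subjects that achieve Chronic CTI Success, defined as persistent bi-directional electrical block across the CTI", assessed at the 75-day remap. SAP 2.4.7 keeps the same denominator: "The proportion of attempted subjects that achieve Chronic CTI Success". It is reported in SAP Table 11.

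**CTI durability.** Protocol 6.4, item 3, says: "Durability is defined as unaltered integrity of each such lesion assessed at the Remapping Procedure". SAP 2.4.6.2 lists it as "Durability of the CTI and/or other extra-PV lesion set(s), when applicable". Neither document prints a denominator. It is reported in SAP Table 13, in one row whose label covers the CTI and other extra-PV lesion sets.

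**Derivations in SAP 2.5.** Both variables start from "IF CTI lesion durable ='Yes" on the follow-up mapping form. One then returns "Durability of CTI at remap = 'Yes" and the other "Chronic CTI at 75d remap ='Yes". In both, an entry of No returns No. Acute CTI Success, in the same section, is the only one of the three CTI endpoints that uses index-form items: "COUNT IF [CTI isolated/Blocked='Yes' AND CTI Attempted='Yes".

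**Missing data.** SAP 2.5 opens by making a derived criterion missing when any component is missing. SAP 2.1.2 analyses available data only.

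**The concern.** The two endpoints answer different questions. Chronic CTI Success asks how often an attempt ends in lasting block, so an attempt that never achieved block is a failure. Durability asks whether a lesion that was made has stayed intact, and a line that never blocked has no integrity to keep or lose. A single rule that ignores the index result cannot tell these two situations apart.

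The stake is the evidence on FARAFLEX. Protocol 5.3 gives its controlled introduction as the purpose of the study, and a line between the inferior vena cava and the tricuspid valve is one of its three intended uses (Protocol 2.2). CTI ablation is at the investigator's discretion in a study of up to 40 subjects, so the CTI denominator may be small, and one or two misplaced subjects would then show. The results are meant to inform later studies.

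**Working it through.** The plan states no CTI figure to reproduce, so the check compares the rules and then works through the denominators.

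**Step 1: rules side by side.**

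| | Durability of CTI | Chronic CTI |
|---|---|---|
| Source item | CTI lesion durable | CTI lesion durable |
| Item = Yes | Yes | Yes |
| Item = No | No | No |
| Item blank | missing | missing |
| Uses CTI attempted? | no | no |
| Uses CTI blocked at index? | no | no |

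The rules are the same apart from the output name.

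**Step 2: the case that separates the endpoints.** Take a remapped subject with CTI attempted but not blocked at index. Such subjects do reach assessment, because Protocol 3.12.5 calls for remap evaluation of patients who received CTI ablation, without requiring acute block. The definitions, with durability read as applying to lesions that achieved block, require Chronic CTI = No (counted) and durability = not applicable (excluded).

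| Entry in the item | Chronic CTI | Durability |
|---|---|---|
| No | right | wrong: acute failure counted as a lost lesion |
| Blank | wrong: attempted failure dropped | right |
| Yes | wrong | wrong |

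No entry makes both right.

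**Step 3: size.** Let *m* be the number attempted and remapped, *a* the number of these not blocked at index, and *k* the number blocked at index and still blocked at remap.

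- Chronic CTI Success = *k*/*m*
- Durability = *k*/(*m* − *a*)
- Difference = *k*·*a* / [*m*(*m* − *a*)]

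Illustration, with assumed counts: *m* = 20, *a* = 2, *k* = 16.

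- Chronic CTI Success = 16/20 = 80.0% (exact 95% CI 56.3 to 94.3%)
- Durability = 16/18 = 88.9% (exact 95% CI 65.3 to 98.6%)
- Difference = 16 × 2 / (20 × 18) = 32/360 = 8.9 points

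If the item is left blank for the two acute failures, both variables come out at 16/18 and Chronic CTI Success is 8.9 points too high. If it is entered No, both come out at 16/20 and durability is 8.9 points too low.

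Range, assuming one acutely blocked CTI reconnects, so *k* = *m* − *a* − 1:

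| *m* | *a* = 0 | *a* = 1 | *a* = 2 | *a* = 3 |
|---|---|---|---|---|
| 10 | 90.0 / 90.0 | 80.0 / 88.9 | 70.0 / 87.5 | 60.0 / 85.7 |
| 20 | 95.0 / 95.0 | 90.0 / 94.7 | 85.0 / 94.4 | 80.0 / 94.1 |
| 25 | 96.0 / 96.0 | 92.0 / 95.8 | 88.0 / 95.7 | 84.0 / 95.5 |

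Each cell gives Chronic CTI Success / durability, in percent. With *a* = 0 the endpoints coincide and the shared rule does no harm.

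**The case against.** - **The durability denominator is inferred.** This stands. Neither document says that it is limited to CTIs blocked at index. If it covered every ablated CTI, one rule could serve both variables, and the overlap would come from the protocol rather than from the programming. Against that, integrity can be unaltered only if it was once present, the endpoint applies only where applicable, and SAP 2.5 uses veins isolated at index as the denominator for the corresponding vein-level proportion. The broader reading would also make the two CTI endpoints redundant, and a blank entry would still remove an attempted subject from Chronic CTI Success.
- **The direction depends on a form not in the documents.** This stands. If sites enter No for an attempted CTI that was never blocked, Chronic CTI Success is right among remapped subjects and only durability is affected. The SAP gives no instruction for this case.
- **A reader might infer that the two table rows will always print the same number.** The documents do not support this. SAP 2.5 also derives durability for the mitral isthmus, roof line and posterior line, and the single Table 13 row may pool them with the CTI. The two CTI variables are identical; the printed rows need not be.
- **A reader might infer that every attempted, unblocked CTI makes one variable wrong.** That holds only for remapped subjects. Without a remap both variables are missing. That is correct for durability, and for Chronic CTI Success it follows the available-data rule.
- **The stakes are limited.** Both endpoints are descriptive and neither is primary. Acute CTI results are shown as n/N in Tables 4 and 13, so acute failures are visible there. This bears on priority; it does not make the derivation right.

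**Conclusion.** As written, SAP 2.5 does not enforce the attempted-subject denominator that Protocol 6.5 and SAP 2.4.7 state for Chronic CTI Success, and it gives CTI durability the same rule. For a remapped subject whose CTI was attempted but not blocked at index, that rule cannot be right for both variables, provided durability is read as applying to lesions that achieved block.

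The size cannot be computed from the documents, because they contain no CTI counts. It is zero if every attempted CTI was blocked acutely. In the illustrative range above, one to three acute failures separate the two figures by 3.8 points (25 attempted, one failure) to 25.7 points (10 attempted, three failures). The 8.9-point example is one assumed case, not an estimate of error in this trial. The point should be corrected because it can change a reported result and the repair is small.

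**What to change.** In SAP 2.5:

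1. Derive Chronic CTI Success among remapped subjects with CTI Attempted = Yes. Count success only if the CTI was blocked at index and durable at remap, and failure otherwise.
2. Derive CTI durability among subjects with CTI isolated/Blocked = Yes at index and the CTI assessed at remap.

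In the tables:

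3. Report CTI durability as its own line in Table 13, separate from the other extra-PV lesion sets.
4. In Table 11, beside Chronic CTI Success, give the number attempted but not remapped. Limiting the denominator to remapped subjects is a choice that the protocol wording does not spell out, and this count lets a reader see its effect.

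The cost is two derivation lines, one added table line and one added count. All items needed are already on the index and remap forms, so no new data collection is required.
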